4. TABLE OF EVENTS

The schedule of assessments in Table 2 outlines the specific time points for study assessments.

Table 2. Schedule of Assessments

Assessment ^a	Screening ^b (Day -14 to -1)	Cycle 1 through Last Cycle (Treatment Period)			End of Treatment (EOT) Visit ^d	Follow-up Period ^e
		Day 1 ^c	Day 8	Day 15		
General Assessments						
Informed Consent	X					
Demographics	X					
Medical History	X					
Physical Examination	X	X			X	
Vital Signs, Height and Weight	X	X ^f	X ^f	X ^f	X ^f	
BSA Calculation		X ^j				
Prior/Concomitant Medication Evaluation ^g	X	X	X	X	Until 28 days after the last dose of IP	
Prior/Concurrent Procedures Evaluation ^g	X	X	X	X	Until 28 days after the last dose of IP	
ECOG PS	X	X			X	
Pregnancy Test ^h	X				X	
ECG (12 lead) ⁱ	X					
Survival status						X
Adverse Events		Continuous starting from signing of Informed Consent until 28 days after last dose of IP				
Dexamethasone (every cycle)			X			
Nivolumab Dosing		X				
ABI-009 Dosing: To Start after 2nd Nivo dose			X	X		
Local Laboratory Assessments						
Clinical Chemistry Panel	X	X	X	X	X	
CBC, Differential, Platelet Count	X	X	X	X	X	

Assessment ^a	Screening ^b (Day -14 to -1)	Cycle 1 through Last Cycle (Treatment Period)			End of Treatment (EOT) Visit ^d	Follow-up Period ^e
		Day 1 ^c	Day 8	Day 15		
PT, PTT, INR	X					
Urinalysis	X					
Thyroid function	X	X				
HIV, HBV sAg, HBV cAb, HCV Ab	X					
Fasting Lipids	X	X				
Trough rapamycin level ^k						
Immunohistochemistry for PTEN mutation in archived tumor	X					
Imaging and Efficacy Assessments						
CT/MR ^l	X	Every 6 weeks after C1 D1 for the first year, then every 12 weeks thereafter			X	

- a. Unless otherwise specified, visits must occur within \pm 2 days of the planned visit date.
- b. Screening evaluations to be obtained \leq 14 days prior to enrollment unless specified otherwise.
- c. Day 1 evaluations can be omitted if screening evaluations are performed within 72 hours of Cycle 1 Day 1 except for thyroid and fasting lipids every 12 weeks.
- d. End of Treatment Visit must occur at least 4 weeks (\pm 7 days) after the last dose of ABI-009.
- e. Follow-up for survival and initiation of anticancer therapy can be performed by telephone contact every 12 weeks (+/- 3 weeks) or more frequently if needed, from EOT Visit. All patients that discontinue study drug and have not withdrawn full consent to participate in the study will continue in the follow-up phase for survival and anticancer therapy. This evaluation may be made by record review and/or telephone contact.
- f. Vitals and weight only.
- g. Prior: record all medications taken and procedures done \leq 28 days prior to screening; Concomitant: any medications or procedures after the signing of informed consent.
- h. For females of childbearing potential only. A serum β -hCG pregnancy test must be performed to assess patient eligibility at screening prior to first IP administration (negative results required for IP administration). Urine pregnancy test will be performed at EOT Visit (can be done locally) and as clinically indicated as per institutional guidelines.
- i. ECG to be monitored at screening, and as clinically indicated following standard of care procedures.
- j. Calculated ONLY on C1/D1; to be recalculated only if the weight changes by > 10% in subsequent cycles.
- k. Trough levels of rapamycin will be obtained immediately prior to ABI-009 infusion at Day 15 of the second and third cycles of ABI-009, a week after the first dose in both cycles.
- l. Screening CT/MRI scans must be performed within 28 days prior to study day 1, preferably as close to the day of enrollment as possible. Tumor evaluation by contrast-enhanced CT or MRI of the chest, abdomen, and pelvis will be performed during screening; every 6 weeks (\pm 3 days after C1D1 for the first year then every 12 weeks (\pm 7 days) thereafter until disease progression. EOT visit CT/MRI should be performed only for those patients that discontinue treatment for a reason other than disease progression per RECIST 1.1. If an initial observation of objective response (CR or PR) is made, a confirmation scan should be done at 6 weeks after initial observation.

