Patients will be evaluated for disease control rate [complete response (CR), partial response (PR), and stable disease (SD)], or progressive disease (PD) by CT imaging. Contrast enhanced MRI can also be used, as long as the same modality is used throughout the study. Baseline scan results can be accepted from outside institutions, but must be done within 4 weeks of starting therapy and must include (as clinically indicated), chest abdominal, and pelvic CT or MRI. The first response assessment by CT or MRI scans documenting target lesions will be done 6 weeks after first treatment and should be repeated every 6 weeks for the first year, then every 12 weeks thereafter until the end of treatment. If an initial observation of objective response (CR or PR) is made, a confirmation scan should be done at 6 weeks after initial observation. Scans should continue on schedule regardless of delays in ABI-009 dosing.

The efficacy endpoints, DCR (CR, PR and SD), OR (CR + PR), PFS, and RFS will be determined by a local radiologic assessment using RECIST v1.1. After end of treatment, patients will be followed for survival every 12 weeks (+/- 3 weeks), or more frequently as needed, until death, withdrawal of consent, or the study closes, whichever is the earliest.

Statistical Considerations

Safety Analyses:

Demographic and baseline information (e.g., extent of prior therapy) on study patients will be tabulated. The number of patients studied for the Phase 1 (dose escalation) part of study could range from 12 to 18 evaluable patients, and 22-28 evaluable patients for the Phase 2 (dose expansion) part of the study.

For the Phase 1 part of the study, the following information will be reported for all adverse events observed in the study: dose level, type (organ affected or laboratory determination, such as absolute neutrophil count), severity (by NCI Common Terminology Criteria for Adverse Events (CTCAE) Version 4.03 and most extreme abnormal values for laboratory determinations) and relatedness to study treatment. For each dose the number and percentage of patients experiencing any grade 3, 4, or 5 adverse event will be reported, as well as the number and percentage of patients who experienced selected specific types of adverse events. In addition, the DLTs will be summarized by dose level and the MTD will be determined.

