2.1.3. Exploratory Objectives

- To correlate DCR based on Immune-related Response Criteria (irRECIST) with that based on RECIST v1.1.
- To correlate DCR with PD-L1 and other biomarker expression in patients' tumors
- To correlate DCR with PTEN mutation in patient's archived tumor

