Surgical Resection: After three or more treatment cycles, the principal investigator may recommend surgical debulking, complete surgical removal or a biopsy. If residual disease is present either by histopathological examination or by CT scan/MRI, repeat treatment cycles may be given 2-4 weeks after surgery, if the surgical incision has healed, and if the patient has \leq grade I toxicity.

Resected or biopsied tumors will be analyzed for the effects of this dual therapy on disease control rate, and immune cell trafficking in the tumor microenvironment. Fresh and paraffin embedded tissue blocks will be analyzed by FACS for PD-L1 and other biomarkers, including Tregs, CD8+, CD4+ cells etc. Immunohistochemistry for cyclin G1, cyclin D1 and Ki67 will be conducted to determine the tumor's proliferative state. Histopathologic examination for tumor necrosis and mitotic index will also be determined.

Conditions for Continuation of Treatment in the Presence of Increased Tumor Size by CT scan or MRI Indicating Progressive Disease by RECIST v1.1:

Treatment may be continued if:

1. There are no signs or symptoms indicating unequivocal progression.
2. There is no worsening of ECOG score attributable to progressive disease.
3. There is no tumor growth at critical sites that is life-threatening.
4. Patient signs an informed consent that he/she is aware of alternative therapies but wishes to defer these therapies.
5. There is clinical benefit, as determined by investigator

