5.2.4. Response Assessment

Tumor response will be assessed by CT or MRI scan of the chest, abdomen, and pelvis (CAP); image preparation and evaluation will follow the specifications provided in the RECIST version 1.1. Immune RECIST (irRECIST) will also be obtained. The same modality (CT or MRI) must be used at screening and throughout the study.

CT/MRI scans to be performed at the following frequency:

- ≤2 weeks prior to C1D1 (screening)
- followed by every 6 weeks for the first year; then every 12 weeks until disease progression or unacceptable toxicity. End of Treatment Visit CT/MRI should be performed only for those patients that discontinue treatment for a reason other than disease progression.

An unscheduled scan for suspected disease progression may be performed at any time. However, adherence to the planned imaging schedule is critical regardless of dose delays or unscheduled or missed assessments. Determination of disease progression for clinical management of patients on study will be assessed at the local site. If an initial observation

of objective response (CR or PR) is made, a confirmation scan should be done at 6 weeks after initial observation.

Conditions for Continuation of Treatment in the Presence of Increased Tumor Size by CT scan or MRI Indicating Progressive Disease by RECIST v1.1:

Treatment may be continued if:

1. There are no signs or symptoms indicating unequivocal progression.
2. There is no worsening of ECOG score attributable to progressive disease.
3. There is no tumor growth at critical sites that is life-threatening.
4. Patient signs an informed consent that he/she is aware of alternative therapies but wishes to defer these therapies.
5. There is clinical benefit, as determined by investigator

Table 3. Analyte Listing

Chemistry	Hematology	Coagulation	Urinalysis	Other Labs
Sodium	WBC	PT	Specific gravity	Pregnancy test
Potassium	RBC	PTT	pH	
Bicarbonate	Hemoglobin	INR	Blood	TSH, T3, T4
Chloride	Hematocrit		Protein	HIV
Total protein	MCV		Glucose	HBV sAg
Albumin	MCH		Ketones	HBV cAb
Calcium	MCHC		Microscopic	HCV Ab
Magnesium	RDW			Total Cholesterol
Phosphorus	Platelets			HDL
Glucose	Differential:			LDL
BUN	-Neutrophils			Triglyceride
Creatinine	-Lymphocytes			PD-1\PD-L1
Total bilirubin	-Monocytes			
Alkaline phosphatase	-Eosinophils			
AST (SGOT)	-Basophils			
ALT (SGPT)				
Amylase				
Lipase				

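### The plan gives conflicting end points for scheduled tumour scans; if scans stop at progression, the irRECIST analyses have no scheduled data after the first PD

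*Combined protocol and SAP*

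**What the plan says.** **When scheduled scans end.** The synopsis (Overview of Key Efficacy Assessments) says that scans "should be repeated every 6 weeks for the first year, then every 12 weeks thereafter until the end of treatment". The imaging row of Table 2 reads "Every 6 weeks after C1 D1 for the first year, then every 12 weeks thereafter" and shows no stop at progression. Footnote l to that row adds one: scans run "thereafter until disease progression". Section 5.2.4 has "then every 12 weeks until disease progression or unacceptable toxicity".

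**The end-of-treatment scan.** Footnote l limits it to patients who "discontinue treatment for a reason other than disease progression per RECIST 1.1", and Section 5.3 says the same. The only confirmation scan in the plan is for a first CR or PR; none is specified after PD. Section 5.2.4 permits an unscheduled scan at any time when progression is suspected.

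**When treatment ends.** The synopsis, Section 2.3 and Section 5.2.4 each carry a list headed "Conditions for Continuation of Treatment in the Presence of Increased Tumor Size by CT scan or MRI Indicating Progressive Disease by RECIST v1.1", with five conditions under which treatment may go on. Section 6.1 continues therapy until progression is clinically unequivocal, among other reasons to stop.

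**Where irRECIST is used.** Section 2.2.2 makes DCR, PFS and RFS secondary endpoints under both RECIST v1.1 and irRECIST. The first exploratory objective in Section 2.1.3 is "To correlate DCR based on Immune-related Response Criteria (irRECIST) with that based on RECIST v1.1". Section 8.4 analyses that comparison with descriptive statistics and comparative Kaplan-Meier curves.

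**The concern.** Section 5.2.4 permits treatment beyond RECIST PD and, a few lines earlier, ends scheduled imaging at progression. A site working from Table 2 and Section 5.2.4 could reasonably stop scanning a patient who is still being treated. Any later stabilisation or shrinkage in that patient would then go unrecorded unless an optional scan happened to catch it.

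That matters for the irRECIST analyses, because what happens after a first RECIST PD is one of the places where the two criteria can diverge. If the schedule collects nothing there, the plan cannot tell true agreement from agreement produced by stopping the scans. Scans that were not done cannot be recovered at the analysis stage.

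**Working it through.** The plan states no figure for agreement between the criteria, so there is none to reproduce. The check is a comparison of the rules, the timing that follows from the schedule, and an illustration for DCR.

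**1. The scan rules side by side**

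| Place | Scheduled scans end at | After first RECIST PD, still on treatment |
|---|---|---|
| Synopsis | End of treatment | Scans continue |
| Table 2, row | No stop shown in the treatment columns | Scans continue |
| Table 2, footnote l | Disease progression | No scheduled scan, if progression means RECIST PD |
| Section 5.2.4 | Disease progression or unacceptable toxicity | As footnote l |

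The stop clauses in footnote l and Section 5.2.4 do not name a criterion. The next sentence of footnote l, on the end-of-treatment scan, does name RECIST 1.1, which makes RECIST PD the natural reading.

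**2. Timing**

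ABI-009 starts on Day 8 of Cycle 2, and cycles last 21 days.
- First ABI-009 dose: 21 + 8 = study day 29.
- Second dose: 21 + 15 = day 36.
- First scan, six weeks after first treatment: 1 + 42 = day 43.

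A PD at the first scheduled scan therefore follows at most two ABI-009 doses. Treatment may run to 18 cycles, with ABI-009 twice in each of Cycles 2 to 18: 17 × 2 = 34 doses. A patient who continued past a first-scan PD could receive up to 34 − 2 = 32 further doses with no scheduled scan under the footnote l reading. This is an upper limit, not an expectation.

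**3. Which endpoints are affected under that reading**

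- *PFS and RFS by irRECIST.* Every patient treated past a first PD is affected, at whichever scan it occurs. The irRECIST date can differ from the RECIST date only through a different reading of the same scans, or through optional imaging.
- *DCR by irRECIST.* A patient with SD or better at the first scan counts as controlled under both criteria, so mainly patients with PD at the first scan can change. (Section 8.8.2 places the word confirmed ahead of CR, PR and SD. If that were applied to SD, some patients with PD at the second scan would also come into scope.)

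**4. Illustration for DCR if scans did continue**

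Inputs:
- n = 22 to 28, the Phase 2 size in Section 3.1.
- q, the share with PD at the first scan: 3/13 = 23%, the PD share in the earlier trabectedin and nivolumab study in Section 1.1.3, with 60% as an assumed upper value.
- r, the share of those who would count as controlled under irRECIST if scanned again: assumed 5% to 20%. The documents give no value.

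Formulas: expected discordant patients = n × q × r; agreement = 1 − q × r. Kappa = (agreement − pe)/(1 − pe), where pe = p1 × p2 + (1 − p1)(1 − p2), p1 = 1 − q and p2 = 1 − q + q × r.

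| q | Discordant patients | Agreement | Kappa |
|---|---|---|---|
| 23% | 22 × 0.23 × 0.05 = 0.25 to 28 × 0.23 × 0.20 = 1.3 | 98.9% to 95.4% | 0.97 to 0.86 |
| 60% | 22 × 0.60 × 0.05 = 0.7 to 28 × 0.60 × 0.20 = 3.4 | 97% to 88% | 0.94 to 0.76 |

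If scheduled scans stop at the first PD and no optional scan is done, discordance arising from later scans is zero by construction, whatever r is.

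**The case against.** **Scans and treatment may be meant to end together.** Section 5.2 ends therapy at progression or unacceptable adverse events, in words close to the scan clause in Section 5.2.4. On that reading a patient kept on treatment keeps being scanned, in line with the synopsis and the Table 2 row. This stands as a possible reading. It is why a reader who infers that irRECIST cannot be followed past the first PD goes too far: that holds under one reading only. It does not remove the conflict, because footnote l and Section 5.2.4 do not say this.

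**Unscheduled scans are allowed.** They are, but they are optional and triggered by suspected progression, so they are not a systematic look for later stabilisation. A patient treated past PD who then stops for another reason would have an end-of-treatment scan; that is a single late image.

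**Agreement would be high anyway.** For DCR this largely stands. A reader might infer that near-complete agreement would be a product of the schedule; the illustration does not support that, since agreement is 88% to 99% even with continued scanning. The narrower point remains: the exploratory objective is to measure the discordance, and the restrictive rule removes one source of it.

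**The affected group could be large.** A reader might multiply enrolment by the early progression shares in the Introduction: 3 of 13 in the earlier combination study, or 45% and 72% (one minus the 12-week PFS of 55% and 28%) in the cited pembrolizumab trial. The documents do not support that count. Those shares come from other treatments, and the 12-week figures include deaths. Only patients who meet all five continuation conditions are affected. Patients who progress before ABI-009 are replaced and left out of the analysis (Section 8.3).

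**The stakes are modest.** All analyses are descriptive, the comparison is exploratory, and Section 8.3 names RECIST v1.1 only. That limits the weight of the point. Even so, Section 2.2.2 and the synopsis do apply irRECIST to DCR, PFS and RFS.

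**Conclusion.** The point holds as an internal conflict with a conditional consequence. The synopsis schedules scans to the end of treatment; footnote l and Section 5.2.4 schedule them to progression, while treatment may go on past RECIST PD. If the latter two are followed, and progression is read as RECIST PD, patients treated past first PD have no further scheduled scan. The irRECIST endpoints and the comparison with RECIST then lack scheduled post-PD data.

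The effect is mainly on irRECIST PFS and RFS. For DCR it is small in absolute terms: about 0.25 to 3.4 patients among 22 to 28, on assumed reclassification rates of 5% to 20% and first-scan PD shares of 23% to 60%. The number of patients treated past PD cannot be derived from the documents. The conclusion does not rely on any particular irRECIST rule for confirming PD, since the documents do not state one. It is worth correcting because the loss cannot be repaired afterwards.

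**What to change.** Reconcile the three places by using the synopsis end point in Table 2 footnote l and Section 5.2.4, so that scheduled scans continue while the patient is on study treatment, including after a first RECIST PD. State that the first RECIST PD date is kept for all RECIST endpoints and that later scans are used for irRECIST only. Beside the RECIST and irRECIST agreement table, report how many patients had a scan after first PD, so that readers can see how much of the agreement was open to observation.

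The cost is a wording change in two places, one added line in the reporting, and a few additional scans in patients treated past PD, which the synopsis already schedules.

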5. PROCEDURES

5.1. Screening Evaluations

This study will be conducted at a single center, the Sarcoma Oncology Research Center, Santa Monica CA, USA. Each patient who enters into the screening period for the study receives a unique patient identification number before any study-related procedures are performed. The patient identification number will be assigned. This number will be used to identify the patient throughout the clinical study and must be used on all study documentation related to that patient.

The patient identification number must remain constant throughout the entire clinical study; it must not be changed after initial assignment, including if a patient is rescreened.

Before patients may be entered into the study, the Sponsor requires a copy of the site's written IRB/IEC approval of the protocol, informed consent form, and all other patient information and/or recruitment material, if applicable. A signed and dated Institutional Review Board (IRB) approved informed consent form (latest approved version) must be obtained from each patient prior to performing any study-specific procedures. All patients or legally acceptable representatives must personally sign and date the consent form before commencement of study-specific procedures. Adverse Events are to be collected for a patient once they have signed the informed consent.

Screening evaluations will be performed for all patients to determine study eligibility. These evaluations must be obtained ≤ 14 days prior to enrollment. Any questions regarding patient eligibility should be directed to AADI or other sponsor-nominated representatives or designees for approval.

The following procedures are to be completed during the screening period, after signed informed consent has been obtained, designated in the Schedule of Assessments, Table 2.

- Demographics (if allowed by local regulations, date of birth, sex, race, and ethnicity)
- Physical examination as per standard of care (including physical exam, medical/cancer history, ECOG performance status assessment, height, weight)
- Prior/concomitant medication evaluation: all medications taken ≤ 28 days prior to screening
- Prior/concurrent procedures evaluation: all procedures done ≤ 28 days prior to screening
- Vital signs (eg, blood pressure, pulse, respiration rate, temperature)
- ECG
- Adverse event assessment
- Local Laboratory Assessments: chemistry, complete blood count (CBC), differential, platelet count, coagulation, urinalysis, thyroid function, pregnancy

test (women of child-bearing potential, includes tubal ligations), HIV, hepatitis B surface antigen, hepatitis C antibody, fasting lipids

- Urinalysis (a urine dipstick may be used)
- CT or MRI, must be performed within 2 weeks prior to study day 1, preferably as close to the day of enrollment as possible
- Immunohistochemistry for PTEN mutation on patient's archived tumor

A patient is considered enrolled when the investigator decides that the patient has met all eligibility criteria. The investigator is to document this decision and date, in the patient's medical record and in/on the electronic case report form (CRF).

All screening tests and procedures must be performed within 14 days of study day 1, unless specified otherwise in the study procedures listed in [Section 4](#).

